## **List of Abbreviations**

AE	adverse event
ADE	adverse device effect
bpm	beats per minute
CI	confidence interval
СРАР	Continuous Positive Airway Pressure; bCPAP is 'bubble' CPAP
FiO 2	Fraction of Inspired Oxygen
S	second
SAE	serious adverse event
SADE	serious adverse device event
SpO 2	Oxygen saturation measured by transcutaneous pulse oximetry
SSI	significant safety issue
USADE	unanticipated serious adverse device event
USM	urgent safety measure
VDL1.1	Van Diemen's Land 1.1 algorithm

## 1. ADMINISTRATIVE INFORMATION

Protocol: v1.5; 6/8/2022 ClinicalTrials.gov register Identifier: NCT05508308

## 1.1 Document Version History

Version Date	Version	Author	Signature	Change Description	Reason/Comment
	1.0			Initial release.	Not applicable.

## 2. STUDY SYNOPSIS

A randomised cross-over trial of manual versus automated control of oxygen (OxyMate) for preterm infants on Continuous Positive Airway Pressure (CPAP). This trial will use an established technology (automated

oxygen titration algorithm, VDL1.1) partnered with a low-cost CPAP device in a low-resource setting. It will involve preterm infants requiring CPAP respiratory support with allocation to OxyMate or manual oxygen control for consecutive 24 h periods in random sequence.

The trial will be conducted at two study sites University College Hospital Ibadan (UCH) and Sacred Heart Hospital Lantoro (SHHL) in Southwest Nigeria. The planned sample size is to collect 40 complete studies. The trial is expected to have a duration of 20 weeks. Each child will be enrolled for approximately 2 days.

The aim of this study is to investigate the safety and potential efficacy of OxyMate automated oxygen control compared to manual control for preterm babies (<34 weeks or <2kg if gestation unknown) on CPAP, and explore feasibility and appropriateness of this technology in Nigeria.

[figure not shown]

Figure 1: Trial design

## 2.1. Primary Objective and Outcome

The primary objective of this trial is to evaluate the impact of OxyMate on safe oxygen saturation targeting compared to manual control of oxygen for preterm infants in Nigeria.

The primary outcome is: Proportion of time (over total recorded time) in the target  $SpO_2$  range (91-95%, or 91-100% when in room air). This will be measured as percent time, where the denominator is usable time, excluding all periods during which the  $SpO_2$  values are missing.

Secondary outcome for the primary objective: Proportion of time (over total usable time) in SpO2 target range (91-95%) when receiving supplemental oxygen. This will be measured as percent time when in oxygen.

2.2. Secondary Objectives and	
OBJECTIVE	OUTCOME & OUTCOME MEASURE
To evaluate whether OxyMate	Proportion of time (over total usable time) with SpO 2 <90%
prevents time in, and episodes of,	(hypoxaemia). This will be measured as percent time.
hypoxaemia compared to manual	Proportion of time (over total usable time) with SpO 2 <80% (severe
control of oxygen.	hypoxaemia). This will be measured as percent time.
	Frequency of 30s episodes with SpO 2 continuously <80% (severe
	hypoxaemic episodes). Measured as mean number of episodes per
	hour.
	Duration of episodes with $SpO_2$ continuously <80% for manual and
	automated control epochs. Measured in seconds.
To evaluate whether OxyMate	Proportion of time (over total usable time) with $SpO_2 > 96\%$ when
prevents time in, and episodes of,	receiving supplemental oxygen (hyperoxaemia). Measured as percent
hyperoxaemia compared to	time when in oxygen.
manual control of oxygen.	Proportion of time (over total usable time) with $SpO_2 > 98\%$ when
	receiving supplemental oxygen (severe hyperoxaemia). Measured as
	percent time when in oxygen.
	Frequency of 30s episodes with $SpO_2$ continuously >96%
	(hyperoxaemic episodes). Measured as mean number of episodes per hour.
	Dduration of episodes with SpO 2 continuously >96% for manual and automated control epochs. Measured in seconds.
To evaluate whether OxyMate	Frequency of manual $FiO_2$ adjustments in both manual and automated
reduces nursing workload	arms. This is measured as mean number of FiO 2 adjustments/hour.
compared to manual control of	
oxygen.	
To evaluate whether OxyMate is	Number and duration of periods of no $FiO_2$ increment for $\geq 30s$ with
safe compared to manual control	$SpO_2 < 80\%$ (i.e. failure to respond to severe hypoxaemia). Measured
of oxygen.	as mean number of episodes per hour, and mean duration per
	episode.
	Number and duration of periods with $SpO_2 < 80\%$ for $\ge 30s$ with any
	bradycardia (heart rate <100 bpm). Measured as mean number of
	episodes per hour, and mean duration per episode.
	Number of OxyMate malfunction events
To evaluate whether OxyMate is	Score on User Survey questions using Likert scale.
acceptable and feasible to	
healthcare workers.	
To evaluate the cost of OxyMate.	Total costs of prototype system (Diamedica +/- oxygen automation)
To evaluate participants duration	Duration of time on CPAP with supplemental oxygen. Measured in
of CPAP and oxygen therapy.	hours.
	Duration of time on CPAP in room air. Measured in hours.
Te queluete perticipant aliginal	Duration of time on low-flow oxygen therapy. Measured in hours.
To evaluate participant clinical	Final discharge outcome. Measured as categorical outcome (died in
outcomes	hospital, discharged well, discharged against medical advice, ongoing
	admission, other).
	Length of stay. Measured in days.

## 2.2. Secondary Objectives and Outcomes

## 2.3. Study Population

Preterm infants <34 weeks or <2 kg birthweight if gestation unknown, on CPAP and supplemental oxygen.

### Inclusion criteria:

• ≥12 hours old

- Receiving CPAP support and supplemental oxygen (FiO2 >0.21) for respiratory insufficiency
- Projected requirement for CPAP and oxygen therapy for >48 hours

### Exclusion criteria:

- Deemed likely to fail CPAP in the next 48 hours, and would otherwise qualify for surfactant therapy and/or mechanical ventilation at initial assessment were it available: SpO2 <85% with FiO2 >0.50 on CPAP 8 cmH2O, clinical features of hypercapnic respiratory failure (hypoventilation, reduced level of alertness)
- Deemed clinically unstable or recommended for palliation by treating team
- Cause of hypoxaemia likely to be non-respiratory e.g. cyanotic heart disease
- Informed consent from parent/guardians not obtained

## 2.4. Intervention

**Automated oxygen control arm (OxyMate):** Automated control of oxygen therapy partnered with CPAP delivered as per standard practice. The automated oxygen control set-up (OxyMate) will consist of: continuous pulse oximetry input, a computer algorithm (VDL1.1) that calculates changes to delivered FiO2 based on the input SpO2, and a mechanism to automatically effect changes to delivered FiO2. The system will target an SpO2 of 93% (mid-point of the target range). There will be several embedded safety mechanisms, including the ability to manually over-ride OxyMate at any stage. Pulse oximeter alarms will be as for the manual control arm, with additional automated system alarms in place.

**Manual oxygen control arm:** Oxygen therapy delivered with CPAP as per standard practice, except for the addition of continuous pulse oximetry. Nursing staff will make manual adjustments to  $FiO_2$  provided to infants on CPAP. Oxygen saturations (SpO2) will be monitored by continuous pulse oximetry, and nurses asked to target the range of SpO2 91-95%. Pulse oximeter alarms will be set to alert nurses to periods of hypoxaemia (SpO2<88%) and hyperoxaemia (SpO2>96%).

## 2.5. Randomisation and Blinding

An independent statistician will prepare the randomisation schedule using a computer generated algorithm, with stratification by health facility. Infants will be randomised in a 1:1 ratio, using blocked randomisation.

Given the nature of the intervention blinding is not possible and this will be an open label trial.

## 2.6. Sample Size

To detect a difference in the proportion of time spent in target range between treatment groups of at least 10%, and assuming a similar (~10%) standard deviation of the paired difference to the previous studies conducted using the automated algorithms, with a power of 0.9 and  $\alpha$  of 0.05 would require a sample of 13 infants. To adequately test the equipment with a range of infants and staff members and obtain meaningful feedback on acceptability, we will aim to recruit 40 infants (15-30 per site).

No infants will be excluded post-randomisation. However, infants no longer requiring CPAP during the crossover study period, or having SpO2 consistently>95% for 4 hours when receiving room air, will contribute 'incomplete' data (i.e. only contributing data up until the point they ceased CPAP, or until the point at which SpO2 goes above and remains above 95% consistently for 4 hours without supplemental oxygen), and another infant enrolled to reach a total of 40 complete studies.

## 2.7. Study Procedures

Infants will be managed with each mode of control for 24 hours, prior to crossing over to the other mode of control. Change over will simply involve flicking the computer switch from manual to automated control (or vice versa) and will be enacted immediately. It will not require any adjustment or interruption of the CPAP and it will not involve additional action from clinical staff. While FiO2 adjustments have their effect relatively

#### Statistical Analysis Plan

rapidly, we will drop the first hour of data after switching modes from analysis (washout) to avoid contamination between arms.

For infants in manual control, nursing staff are asked to target SpO2 91-95%, with pulse oximeter alarms set at SpO2<88% and SpO2>96%. Treating teams will have access to continuous pulse oximetry display of SpO2 and pulse rate.

For infants on OxyMate, nursing staff will be asked to manage babies as per routine care, including SpO2 targeting. They will be instructed that manual override of OxyMate is possible at any time by manually turning one of the flow meters. Continuous pulse oximetry display will be available, in addition to a laptop screen displaying pulse rate, SpO2 and alarm messages. Disabling OxyMate indefinitely will be possible by pressing a large button on the laptop touch screen (and will be automatically recorded in the computer log).

During routine cares (e.g. nappy changes or nasogastric tube reinsertion), nursing staff will be provided the option to manually override OxyMate, but it is not prescribed to do so, and the Van Diemen's Land (VDL1.1) algorithm has been found to be effective during care times.

Full details of the background to the trial and its design are presented in the protocol.

## 3. GENERAL STATISTICAL METHODOLOGY

## 3.1. Objectives of Analysis Plan

This analysis plan covers the analysis of the primary and secondary objectives.

## 3.2. Analysis Software

All analyses will be done in Stata (version 17 or higher).

## 3.3. Definition of analysis populations

All participants who are randomised will be included in the analysis, even if they did not complete the study. Data will be analysed according to the intention to treat principle which will include all participants who were randomised in the treatment arm they were randomised to.

## 3.4. Definitions related to Adverse Events (AEs)

	Definition	Effect	Mechanism linking device to effect
Adverse Device Effect (ADE)	Any untoward and unintended response to a medical device. This definition includes any event resulting from insufficiencies or inadequacies in the instructions for use or the deployment of the device.	
 
Death and serious adverse event (SAE)
 
Prolonged hypoxaemia
 
Prolonged hyperoxaemia
 
	
 
In OxyMate automated mode:
 
Failure to respond to SpO2 deviation, resulting in prolonged hypoxaemia or hyperoxaemia
 
Failure of alarms to alert health workers to rising oxygen requirement
 

Device deficiencies	Inadequacy of a medical device with respect to its identity, quality, durability, reliability, safety or performance. Device deficiencies include	
 
Prolonged (>30 s) episode of severe hypoxaemia (SpO2 <80%) without an increase in FiO2
 
Prolonged (>30 s)
 
	
 
Errors in:
 
Algorithm – failure to respond correctly to SpO2 data
 
Servomotor controller – failure to correctly adjust oxygen/air flow
 

	Definition	Effect	Mechanism linking device to effect			
	malfunctions, use errors and inadequate labelling.	episode of severe hyperoxaemia (SpO 2 >98% when receiving oxygen) without a decrease in FiO 2	
 
Alarms – failure to detect/alert to errors
 
			
Adverse Event (AE)	Any untoward medical occurrence in a participant administered a medicinal product and that does not necessarily have a causal relationship with this treatment.	
 
Death
 
Other clinical deterioration, new illness, or new injury
 
				
Serious Adverse Event (SAE)	
 
a life-threatening illness
 
a permanent impairment
 
prolonged hospitalisation
 
medical or surgical interv
 
	nt of a body structure or a body function, or				
Serious Adverse Device Event (SADE)	-	to a body structure or a body function An adverse device effect that has resulted in any of the consequences of a SAE.				
Unanticipated Serious Adverse Device Effect (USADE)	-	A serious adverse device effect which by its nature, incidence, severity or outcome has not been identified in the current version of the risk analysis report.				
Significant Safety Issue (SSI)	-	A safety issue that could adversely affect the safety of participants or materially impact on the continued ethical acceptability or conduct of the trial.				
Urgent Safety Measure (USM)	-	immediate hazard to a pa Note: This type of signific by either the investigator	e taken in order to eliminate an articipant's health or safety. ant safety issue can be instigated or sponsor and can be king approval from HRECs or			

#### 3.5. Adjustment for Multiplicity

No adjustment for multiplicity will be made.

## 3.6. Interim Analyses

There will be no interim analysis.

## 3.7. Handling of Missing Data

The greatest risk of missing data will be from missing pulse oximetry reading due to disconnection or poor perfusion. Previous studies suggest that the proportion of SpO2 readings missing will be 2-4%, and very likely evenly balanced in the two study arms.

No imputation of missing data will be done. The proportions of time in each SpO2 range will be calculated using the denominator of usable time, i.e. without inclusion of time with missing SpO2 readings. For incomplete studies (i.e. infants who do not complete both phases) we will include all data of continuous pulse oximetry up to the point of cessation or ineligibility but exclude data obtained after the infant discontinued or was no longer eligible (e.g. infants who cease CPAP or who have SpO2>95% for 4 hours while in room air). We will record other clinical data (e.g. clinical outcomes and complications) for all infants irrespective of whether or not they completed one or both treatment phases.

## 4. DESCRIPTIVE STATISTICS

## 4.1. Recruitment and Follow-up

We will include a flowchart reporting:

- Number screened
- Number excluded and reasons for exclusion
- Number randomised, and treatment allocation
- Number discontinuing study prior to complete 49 hours and timing and reasons for discontinuation
- Number with complete studies
- Number analysed

## 4.2. Baseline Characteristics

The following variables will be summarised at enrolment into the study:

- Gestation
- Birth weight
- Age in hours
- Diagnosis

Baseline characteristics will be summarised by mean and standard deviations (SDs) for continuous variables, and counts and percentages for categorical variables.

## 4.3. Protocol Deviations

Protocol deviations will be listed. Some infants will cease CPAP or no longer require oxygen. These studies will be considered incomplete. The number of participants with and reasons for incomplete studies will be summarised.

## 4.4. Compliance

The primary and some of the secondary outcomes assess whether health workers comply with the recommendation to titrate  $FiO_2$  such that  $SpO_2$  is maintained within a safe range.

We will report how many of the infants in each of the time periods were receiving the CPAP method they were assigned to for the majority of the time while receiving oxygen. The percentage of time in manual or automated control in each of the periods will be given.

# 5. ANALYSIS OF THE PRIMARY OUTCOME(S)

## 5.1. Main Analysis

Primary outcome: Percent of time (over total recorded time) in the target  $SpO_2$  range (91-95%, or 91-100% when in room air).

Cross-over studies introduce risks of carry-over and period effects, and we have attempted to account for these in the study design. We consider carry-over effects to be small given that change from one mode of control to the other is instantaneous. We have allowed for a 1-hour change over period where data are not

Statistical Analysis Plan

included in the analysis. Period effects are possible with changes in practice over the study period for each infant but large changes in care over the 48 hour study period are unlikely. The clinical condition of infants will be dynamic and may change over the study period, but the primary outcome of time in target SpO2 range will be comparable irrespective of the clinical course of an infant as long as they remain on oxygen.

We will compare mean percentage time in target SpO2 range (y in code below) between the two 24 h arms of manual and automated control using weighted repeated measures mixed model linear regression adjusting for randomised group, treatment (manual vs automated), period, repeated measure in the same participant and facility (site). All infants will be included in this analysis, even those who do not provide complete studies. The weights will be calculated as the reciprocal of the total time in manual and automated control divided by 24 hours for each period separately. Infants who provide complete studies will have a weight of 1.

The following Stata code will be used:

xtmixed y treatment randomised\_group period site [pw = weight] || participant: period

We will plot the primary outcome across the treatments for individual participants using spaghetti (line) plots. The x-axis will represent manual and automated, while the y-axis will be the percent of time in target range. The colours of the lines will represent the randomisation (which treatment was received first) and complete studies will be indicated with solid lines and incomplete studies with dashed lines.

Secondary outcome for the primary objective: "Proportion of time (over total usable time) in SpO2 target range (91-95%) when receiving supplemental oxygen", measured as percent time when in oxygen, will be analysed in the same way as described for the primary outcome.

In order to understand whether incomplete studies are related to the order in which the treatments were received we will summarise the following:

- The number of infants who were randomised to start on the automated treatment (in Period 1) vs the manual treatment who come off oxygen during the study period
- The number of hours of oxygen treatment received by infants who were randomised to start on the automated treatment (in Period 1) vs the manual treatment

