## 5.3. Subgroup Analyses

In subgroup analysis we will extend this model to test whether the following variables modify the effect of the intervention, by adding an interaction term between the treatment and the subgroup indicator. Each of these subgroups will be assessed separately.

The prespecified subgroups are:

- Gestation (<32 weeks; > 32 weeks)
- Birthweight (<1.5 kg, ≥ 1.5 kg)
- Post-natal age at enrolment (< 24 hours; > 24 hours)
- Baseline FiO2 requirement at enrolment FiO2 <0.3, FiO2 0.3-0.4; FiO2 > 0.4

The following Stata code will be used:

xtmixed y treatment##subgroup randomised\_group period site [pw = weight] || participant: period

Subgroup analyses not be done unless specifically specified. It will be done for the primary outcome and for the secondary outcome of the primary objective.

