#### The Stata code will be:

mepoisson y treatment randomised\_group period site [pw = weight] || participant: period, covariance (unstructured) irr

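### The primary-model weight is the reciprocal of time observed, so shorter, truncated records count more than complete ones

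*SAP*

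**What the plan says.** Section 5.1 specifies a weighted mixed linear model for percent time in target. The weight is set as follows, one period at a time: "The weights will be calculated as the reciprocal of the total time in manual and automated control divided by 24 hours". It adds: "Infants who provide complete studies will have a weight of 1". Short records stay in the model: "All infants will be included in this analysis, even those who do not provide complete studies". Section 3.7 says how far they run: "we will include all data of continuous pulse oximetry up to the point of cessation or ineligibility". Section 2.6 makes these infants additional to the planned number, with "another infant enrolled to reach a total of 40 complete studies".

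The weight enters the code as a probability weight, so a larger value means more influence. It recurs in the subgroup model in section 5.3 ("pw = weight] || participant: period") and in the Poisson model in section 6.3 ("pw = weight] || participant: period, covariance (unstructured) irr"). Sections 6.1, 6.2, 6.5 and 6.6 inherit it by reference to the primary analysis. Sections 6.7 and 6.9 to 6.11 inherit it through the Poisson model, and the mean durations in 6.10 and 6.11 through the primary method. Section 5.2 plans no sensitivity analysis.

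**The concern.** A percentage of time based on a few hours is no more precise than one based on 24 h, and usually less so. A precision argument would therefore lower its weight or leave it alone. The SAP's rule raises it, without a cap as T approaches zero.

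The short records are also selected. They arise when an infant stops CPAP or holds a high SpO2 in room air for 4 hours, and the primary outcome counts 91-100% as in target in room air. Section 5.1 itself plans to examine whether incompleteness depends on treatment order. If it does, this weight enlarges the resulting distortion. What is at stake is precision, and possibly bias, in the primary estimate and in most of the comparative secondary analyses. With no alternative weighting planned, nothing in the outputs would reveal the effect.

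**Working it through.** **1. The plan's own figure.** Reading the rule as w = 1/(T/24) = 24/T gives w = 1 at T = 24 h, as section 5.1 states. The other literal reading, (1/T)/24, gives 0.0017 at 24 h and is ruled out.

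**2. Weights for shorter records.**

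| Hours T | SAP weight 24/T | T/24 |
|---|---|---|
| 24 | 1 | 1 |
| 12 | 2 | 0.50 |
| 6 | 4 | 0.25 |
| 4 | 6 | 0.17 |
| 1 | 24 | 0.04 |

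Both columns satisfy the statement that a complete study has weight 1.

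**3. Influence on the treatment contrast.** The contrast is mainly within infant. With period weights w1 and w2, an infant's paired difference has weight w1·w2/(w1 + w2), which is 0.5 for a complete infant. Take a complete period 1 and a 4 h period 2:
- SAP weight: (1 × 6)/(1 + 6) = 0.857, and 0.857/0.5 = 1.71 times a complete infant.
- T/24: (1 × 1/6)/(1 + 1/6) = 0.143, and 0.143/0.5 = 0.29 times.

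As T falls to zero under the SAP weight, the ratio approaches 1/0.5 = 2 and cannot exceed it.

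**4. Effect on the standard error (SE).** The SAP gives neither the number nor the length of incomplete records, so these are assumptions: 40 complete infants plus some truncated in period 2, and a within-period variance of 25 + 600/T. At 24 h that is 25 + 25 = 50, half of it time-dependent. The paired SD is then √(50 + 50) = 10, matching section 2.6. Generalised least squares with variance components held fixed gives:
- 10 records of 1-12 h: SE 1.85 (SAP), 1.54 (unweighted), 1.46 (T/24). 1.85/1.46 = 1.27, so 27% larger than T/24; 1.85/1.54 = 1.20, so 20% larger than unweighted.
- 5 records of 6-20 h: about 4% larger than T/24. A simpler paired-difference approximation gives 1.54 against 1.52, or 1-2%.
- Variance independent of hours (paired-difference approximation): 1.44 (SAP), 1.45 (T/24), 1.40 (unweighted). There is no penalty relative to T/24, and about 3% relative to no weighting.

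**5. Effect on bias.** Assume 10 truncated records, 8 in automated and 2 in manual control, running 15 points higher, with a true effect of 10. The estimates are about 12.0 (SAP), 11.5 (unweighted) and 10.7 (T/24), so the errors are 2.0, 1.5 and 0.7 points.

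**6. Poisson models.** Section 6.3 defines the outcome as episodes divided by hours, and the code has no exposure term. For N episodes in T hours at rate μ, the log-likelihood term is N·log μ − T·μ = T·[(N/T)·log μ − μ]. Modelling counts with T as exposure is therefore the same as weighting the rate in proportion to T. The SAP weights it by 24/T, in the opposite direction.

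**The case against.** The best defence concerns size. A reader might infer that the shortest records dominate the estimate, since a 4 h record has weight 6 rather than 1/6, a 36-fold ratio. The documents do not support that. The ratio is between raw weights; on the paired scale it is 1.71/0.29, about 6-fold, and one infant's influence is capped at 2. With 10 records of 1-12 h, truncated infants hold about 28% of the paired weight while being 20% of the infants. An infant who stops in period 1 has no paired contrast to up-weight at all.

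It is also fair that entry requires a projected need for CPAP and oxygen beyond 48 hours, so truncated records may be few, and that the design has ample power: section 2.6 needs 13 infants and plans 40 complete studies. Even at an SE of 1.85, a 10-point effect is more than 5 standard errors. The simulations fix the variance components and omit the random slope on period, so they illustrate rather than predict. A reader might also blame the reciprocal for the whole bias in step 5, but 1.5 of the 2.0 points are present without any weighting. These limits stand.

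Two defences of the rule itself do not. An inverse-probability reading fails, because that method up-weights well-observed infants who resemble those lost, whereas this rule up-weights the truncated records themselves. A slip for T/24 is possible, since the weight-of-1 statement fits both, but a programmer following the text would code the reciprocal.

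**Conclusion.** Wrong as written. The direction follows from the text alone: the weight is 24/T and rises as the record shortens, with no rationale given. The size cannot be fixed from the SAP. Under the stated assumptions the loss runs from none relative to T/24 (variance unrelated to hours), through about 4% in the SE (5 records of 6-20 h), to about 27% (10 records of 1-12 h, half the complete-period variance time-dependent). Any bias from unequal informative truncation is enlarged, in the illustration from 1.5 points unweighted to 2.0, but its source is the truncation. The documents do not show that the trial's conclusion would change, nor that short records would control the estimate. The rule still needs correcting, because it sits in the primary analysis, is reused throughout and has no planned check.

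**What to change.** - **Primary, subgroup and percent-time secondary models:** replace the reciprocal with weight = usable SpO2 hours in the period / analysable hours in a complete period. A complete record with no missing readings keeps weight 1, shorter records get less, and the weight matches the outcome's denominator.
- **Sensitivity analysis:** in section 5.2, add the unweighted version of the primary model. It is the better choice if variance turns out not to depend on hours.
- **Poisson models (6.3 and those referring to it):** remove the reciprocal weight and model episode counts with log usable hours as the exposure.
- **Mean durations in 6.10 and 6.11:** state explicitly which weight applies, since they inherit the primary method.

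The cost is a few sentences of SAP text and small changes to the model code, with no new data. The change should be made, and the intended formula confirmed, before the primary model is run.

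### The written model calls carry no small-sample correction: a minor error for the primary interval, a larger one for subgroup tests and possibly sparse episode-duration outcomes

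*SAP*

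**What the plan says.** SAP section 5.1 writes out the Stata code for the primary outcome: an xtmixed call with treatment, randomised group, period and site, ending "period site [pw = weight] || participant: period". The weights are the reciprocal of the fraction of 24 hours observed, and "Infants who provide complete studies will have a weight of 1". All infants enter the model, including those with incomplete studies.

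Section 5.3 repeats the call beginning "xtmixed y treatment##subgroup" for four factors. Gestation, birthweight and postnatal age have two levels; baseline FiO2 has three. Section 5.3 applies these tests to the primary outcome and its companion outcome in oxygen, and sections 6.2 and 6.5 add two more outcomes. Sections 6.10 and 6.11 use the primary method for mean episode duration per infant.

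On size, section 2.6 says "we will aim to recruit 40 infants (15-30 per site"), with replacement of incomplete studies until 40 are complete. Section 3.5 makes no multiplicity adjustment, and section 5.2 plans no sensitivity analysis. The SAP does not mention a t reference, degrees of freedom or a small-sample variance.

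**The concern.** The independent units are infants, about 40 of them. A cluster-robust variance from that many units is biased downwards. A normal reference also ignores the uncertainty in the variance itself. Both make intervals too short and p-values too small.

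For the main treatment contrast, all infants inform the variance and the error is modest. For an interaction, the robust variance leans on the residuals of the smaller subgroup level, which may be a handful of infants. The same holds for an outcome that exists only in infants who had an episode. Because the code is prespecified and no second analysis is planned, nothing else in the report would show the shortfall.

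**Working it through.** **The plan's own figure.** Section 2.6 takes a difference "between treatment groups of at least 10" percentage points, "assuming a similar (~10%) standard deviation of the paired difference", "with a power of 0.9 and" α "of 0.05 would require a sample of 13 infants". A two-sided paired t calculation (noncentral t) gives power 0.883 at 12 infants and 0.911 at 13, so 13 is reproduced. The two-sided normal formula gives (1.960 + 1.282)² × (10/10)² = 10.5, hence 11. The stated size therefore matches t-based inference, not normal-based inference.

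**Assumptions.** (a) With probability weights the command reports a cluster-robust variance and a normal reference. This is assumed default behaviour; the SAP does not state it. (b) Within-infant differences are normal. (c) For the closed form, all n infants are complete (weight 1) and split equally between sequences.

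**Primary contrast, closed form.** The treatment estimate has n − 2 degrees of freedom. The uncorrected robust variance averages (n − 2)/n of the true variance. With the factor n/(n − 1) this becomes (n − 2)/(n − 1). At n = 40:

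- variance ratio 38/39 = 0.974, square root 0.987
- effective critical value 1.960 × 0.987 = 1.935, against 2.024 for t on 38 df
- width ratio 1.935/2.024 = 0.956, so 4.4% too narrow (5.6% without the n/(n − 1) factor)
- type I error P(|t38| > 1.935) = 6.05%

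The normal reference alone accounts for 3.2% of the narrowing (1.960/2.024 = 0.968). With the planned SD of 10, the standard error is 10/√40 = 1.58 points, so the half-width is about 3.06 points instead of 3.20. At n = 50 the width ratio is 0.965 and the error 5.8%.

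**Primary contrast, simulated.** Within-infant differences (100,000 runs) gave 6.1% at n = 40 and 5.7% at n = 50. A weighted mixed model with a random period slope (2,000 runs each, Monte Carlo error about 0.5 points) gave 6.2% with 40 complete infants, 6.0% with 40 complete plus 8 incomplete, and 6.1% with 32 plus 8.

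**Interaction tests.** The SAP gives cut-points but no subgroup sizes, so sizes are assumed. These figures come from simulated within-infant differences for 40 complete infants, with robust variance and normal or chi-square reference. Ranges span separate sets of runs.

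| Smaller level, of 40 | Type I error at nominal 5% |
|---|---|
| 20 | 6.4-6.6% |
| 13 | 6.6-6.9% |
| 10 | 7.7-8.1% |
| 8 | 8.8-9.0% |
| 6 | 10.5-11.1% |

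| FiO2 bands, joint test | Type I error |
|---|---|
| 14/13/13 | 8.7% |
| 18/14/8 | 10.0% |
| 20/14/6 | 11.3% |

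A t test with the ordinary model-based standard error held 4.8-5.2% at every two-level split tried.

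**Episode duration (6.10, 6.11).** An infant without an episode has no mean duration. If n infants contribute to both periods (n is assumed), the closed form gives:

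| n | Type I error | Interval too narrow by |
|---|---|---|
| 20 | 7.3% | 9% |
| 15 | 8.1% | 13% |
| 10 | 10.2% | 20% |

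**The case against.** The strongest reply is that this changes nothing that matters. Forty infants are planned against 13 needed, and a true 10-point difference would lie 10/1.58 = 6.3 standard errors from zero. Extra incomplete infants raise the number of clusters and bring the closed-form narrowing to about 3.5-4%. For the primary conclusion this stands.

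Second, the subgroup figures rest on sizes that the SAP does not give, and three of the four factors have two levels. This also stands. A reader might infer that every subgroup test runs at nearly twice its nominal error. The documents do not support that: reasonably balanced two-level factors give about 6.5-7%. The FiO2 test, however, reaches about 9% even with near-equal bands.

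Third, untreated multiplicity matters more. Four independent tests at an exact 5% already carry 1 − 0.95⁴ = 18.5% chance of at least one false positive. That is so, but section 3.5 declares it openly, whereas the error per test is hidden and adds to it.

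Fourth, the normal reference and robust variance are inferred from the command, and the interaction figures come from within-infant differences for complete infants, not from the full weighted model of section 5.3. Both limits stand. The weighted-model check covers only the main contrast, where it agrees with the closed form.

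**Conclusion.** The concern holds in a limited form. Under the assumed default behaviour, the primary 95% interval is about 4.4% too narrow at 40 complete infants, with type I error about 6%. It would be wrong to read this as a threat to the primary finding, given the margin in sample size.

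The case for a change rests on the interaction tests, which sections 5.3, 6.2 and 6.5 together apply to four factors on four outcomes (16 tests), and on the duration outcomes in 6.10 and 6.11. Their error depends on subgroup sizes and on numbers of contributing infants, neither of which the SAP gives.

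A reader might also infer that the weights or the random period slope must go. This check does not show that. Both affect how incomplete infants count, which is a separate question from small-sample inference.

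**What to change.** Keep the model in sections 5.1 and 5.3 as prespecified. Add that, for all linear outcomes and interaction tests, intervals and p-values use:

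- a t reference, or F for the joint FiO2 test, with degrees of freedom derived from the number of infants who contribute to the contrast (38 for the primary contrast with 40 complete infants and no others);
- a small-sample-corrected cluster-robust variance, with the correction named.

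State the rule for incomplete infants in the degrees of freedom, and report the number of infants in each subgroup level and each duration analysis.

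The cost is a short SAP addition and extended code. If the software does not offer these options together with weights, they must be programmed. The primary interval becomes about 4.6% wider (2.024/1.935 = 1.046), and subgroup intervals widen more. Power for a 10-point difference at 40 infants stays above 99.9%. The 4.8-5.2% error shown above belongs to a model-based t test, so the chosen robust correction should be checked by simulation at small subgroup sizes before it is fixed.
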